13.1 Screening periods

Within 24 hours of symptom onset, participants who are diagnosed as ICH are assigned to either the NBO group or control group. The demographic features, medical history, onset-to-needle time, cranial CT imaging, blood pressure, blood samples and neurological measurements (NIHSS score, mRS score and GCS score) are collected.

13.2 In-hospital periods

The patients who are assigned to the NBO group receive 100% O₂ via oxygen storage face masks (flow rate 8 L/min, 1 hour, four times daily, and 2 L/min via nasal catheter during intermittent periods, for 7 days), otherwise, the patients receive 2 L/min flow of 100% O₂ via nasal catheter for 24 hours daily for 7 days. Secondary stroke prevention follows the 2015 AHA/ASA guidelines for the diagnosis and treatment of acute intracerebral hemorrhage.⁶ Blood samples are collected at 7 days. Cranial CT is performed at 3 days, 7 days and 14 days, and cranial CTP is performed at 7 days after randomization. NIHSS score and GCS score are assessed at 7 days and 14 days after randomization.

13.3 Follow-up periods

Neurological measurements including mRS score and Barthel index are assessed via a telephone interview at 90 days.

14. Adverse events monitoring

14.1 Adverse events (AEs)

All AEs information should be carefully recorded and tracked until properly resolved. AEs in this trial

include pulmonary infections, acid-base imbalances, hematoma expansion, and other severe complications during and after interventions that are considered to be associated with the interventions.

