7.4 Randomization and blinding

All patients are enrolled consecutively and randomized in 1:1 ratio to receive 8 L/min flow of 100% O_2 via oxygen storage face mask or 2 L/min flow of 100% O_2 via nasal catheter using a computer-generated randomization code. This is an open label trial, so we adopt a partial blinding strategy where the clinical assessors are blinded to the treatment allocation but the operators are not. That is, the neurological functional scores and imaging tests are assessed by investigators blinded to the

intervention and grouping. The operators responsible for oxygen interventions to the patients are unblinded.

	STUDY PROTOCOL					
	Enrollment	Allocation		Foll	ow-up	
TIMEPOINT	0 day	0 day	3 days	7 days	14 days	90 days
ENROLLMENT						
Eligibility screen	Х					
Informed consent	Х					
Allocation		Х				
INTERVENTIONS						
NBO		←		\longrightarrow		
Control		←		\longrightarrow		
ASSESSMENTS						
Personal data		Х				
Safety evaluation				Х		
NIHSS	Х		Х	Х	Х	
Glasgow Coma Scale	х		Х	Х	Х	
Barthel index						Х
mRS						Х
Cranial CT	Х		Х	Х	Х	
CT perfusion	Х			Х		

8. Trial Flow Chart

NBO, normobaric hyperoxia; CT, computed tomography; NIHSS, National Institute of Health Stroke Scale; mRS, modified Rankin Scale.

9. Interventions

All patients within 24 hours from definite onset time are screened by the cranial CT to confirm ICH at admission. After diagnosis of ICH, the patient or his certigiers will decide whether to participate in this

trial. If they agree, an informed consent will be signed, and allocation will proceed.

Participants will be allocated into two arms:

The NBO group, undergoing high-flow oxygen via oxygen storage face masks (100% O₂, flow rate 8 L/min, 1 hour, four times daily, and 2 L/min via nasal catheter during intermittent periods, for 7 days) immediately in the emergency room after randomization.

The control group, undergoing 2 L/min flow of 100% O₂ via nasal catheter in the emergency room after randomization, for 24 hours daily for 7 days.

Secondary stroke prevention follows the 2022 AHA/ASA guidelines for the diagnosis and treatment of acute intracerebral hemorrhage. All participants are hospitalized for at least 14 days, and if the hematoma expands and causes cerebral hernia, hematoma aspiration or a decompressive craniectomy will be conducted.

10. Measurements

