11.2 Safety outcomes

The 7-day oxygen pressure (PO₂), the 7-day carbon dioxide pressure (PCO₂) and the 7-day PH value, as well as the death rate and the complication rate (including hematoma expansion, pulmonary infections, acid-base imbalances and so forth) during hospitalization.

12. Study Flow Diagram

13. Study Periods

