14.2 Serious adverse events (SAEs)

SAEs are any untoward medical occurrence (whether related to interventions or not) meeting any of the following criteria: (1) fatal (AEs causes death); (2) life-threatening; (3) causing or prolonging hospitalization; (4) disability or organ function impairment.

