14.4.2 Causal relationship between the event and the intervention

(1) Definitely related

AEs occur during the intervention and/or the AEs disappear when the intervention discontinues. The

occurrence of AEs cannot be explained by factors other than the intervention. Similar AEs re-occur when re-use of the intervention.

(2) Probably related

AEs occur during the intervention and/or the AEs relieve or not when the intervention discontinues. The occurrence of AEs can or cannot be explained by factors other than the intervention. It is not sure similar AEs re-occur when re-use of the intervention.

(3) Probably unrelated

AEs do not occur during the intervention and/or the AEs do not relieve when the intervention discontinues. The occurrence of AEs can or cannot be explained by factors other than the intervention. It is not sure similar AEs re-occur when re-use of the intervention.

(4) Definitely unrelated

AEs do not occur during the intervention and/or the AEs do not relieve when the intervention discontinues. The occurrence of AEs can be explained by factors other than the intervention. Similar AEs do not re-occur when re-use of the intervention.

(5) Unjudged

The judgment cannot be made due to incomplete information.

15. Statistics

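### Section 14.1 admits residual complications as adverse events only if judged associated with the interventions, so non-serious ones can be under-counted or counted differently by arm

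*Combined protocol and SAP*

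**What the plan says.** Section 14.1 says that AEs "include pulmonary infections, acid-base imbalances, hematoma expansion, and other severe complications". The last item is qualified: it covers "other severe complications during and after interventions that are considered to be associated with the interventions". The grammar leaves open whether the qualifier governs only that item or also the three named events.

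Section 14.2 defines SAEs as "any untoward medical occurrence (whether related to interventions or not"), provided that a seriousness criterion is met. Section 14.3 makes causality one of the things evaluated for AEs and SAEs that have occurred. The scale in section 14.4.2 runs down to "4) Definitely unrelated". Section 14.4.1 grades severity from mild to death.

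Section 11.2 makes a safety outcome of "the death rate and the complication rate (including hematoma expansion, pulmonary infections, acid-base imbalances and so forth) during hospitalization". It states no relatedness condition and does not refer to section 14.1.

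On blinding, section 7.4 says: "This is an open label trial, so we adopt a partial blinding strategy". It specifies that "the neurological functional scores and imaging tests are assessed by investigators blinded to the" allocation, and that the staff delivering oxygen are not blinded. Section 16 says that assessors were blinded, without mentioning AE attribution.

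**The concern.** An AE definition should decide what is recorded; relatedness is a property assigned afterwards. Section 14.1 reverses that order for the residual group. An event judged unrelated never becomes an AE, so it cannot appear in a comparison of the arms.

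Randomization protects an all-cause comparison, because background events fall equally on both arms. It does not protect a comparison of events that passed a judgement made with possible knowledge of the arm. If the judgement is equally strict in both arms, events are lost but the ratio is preserved. If it differs, a difference in counted events can appear where none exists, or a real one can be hidden, in either direction.

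Safety is half of the stated objective (section 6). With 48 patients per arm (section 15.1), a few events in or out would visibly change a safety table.

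**Working it through.** The plan gives no complication rate, so there is no figure to reproduce. The check is a comparison of the sections, followed by an illustration on assumed inputs.

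**1. The sections side by side**

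- *14.1 against 14.2.* A residual complication judged unrelated fails the AE definition. If it meets a seriousness criterion, it is nevertheless an SAE. The plan thus allows SAEs that are not AEs.
- *14.1 against 14.3 and 14.4.2.* Causality is to be graded on events already accepted as AEs, with two unrelated grades. A residual event that is not an SAE cannot sensibly hold either grade, since association was the condition of entry. The three named events (if the qualifier does not reach them) and SAEs can hold them.
- *14.1 against 14.4.1.* The residual item is also limited to severe complications, although section 14.4.1 has mild and moderate grades. A moderate residual event is left out by the word severe, not by attribution.
- *11.2 against 14.1.* Both name the same three events. Section 11.2 then ends with an open-ended phrase that it does not define, and section 14.1 is the only place that describes what else counts. Filling one from the other is plausible but not stated.
- *Who judges.* Sections 7.4, 14.3 and 16 do not name the person judging causality or say whether that person is blinded.

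**2. Illustration**

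Inputs:
- 48 patients per arm (section 15.1).
- Assumed: true rate p of residual complications not captured as SAEs, equal in both arms, at 10%, 20% or 30%.
- Assumed: probability a that such an event is judged associated.

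Expected counted events per arm = 48 × p × a. With equal p, the counted ratio is a(NBO)/a(control).

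| p | no filter (a = 1), each arm | a = 0.5 in both arms | a = 0.8 NBO v 0.4 control |
|---|---|---|---|
| 10% | 4.8 | 2.4 v 2.4 | 3.8 v 1.9 |
| 20% | 9.6 | 4.8 v 4.8 | 7.7 v 3.8 |
| 30% | 14.4 | 7.2 v 7.2 | 11.5 v 5.8 |
| ratio | 1.0 | 1.0 | 2.0 |

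Equal attribution halves the count but leaves the ratio at 1.0. Attribution of 0.8 v 0.4 gives a ratio of 2.0 and differences of 4, 8 and 12 percentage points. Swapping the two probabilities gives 0.4/0.8 = 0.5.

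**3. Effect on a whole complication rate**

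Assume further that 25% of patients in each arm have a named event, independent of the residual events and not filtered, and that section 11.2 is filled from section 14.1. The proportion with any counted complication is 1 − (1 − 0.25)(1 − p × a).

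- p = 10%: 1 − 0.75 × 0.92 = 31% v 1 − 0.75 × 0.96 = 28%; RR 1.11
- p = 20%: 1 − 0.75 × 0.84 = 37% v 1 − 0.75 × 0.92 = 31%; RR 1.19
- p = 30%: 1 − 0.75 × 0.76 = 43% v 1 − 0.75 × 0.88 = 34%; RR 1.26

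With a wider gap of 0.8 v 0.2, the residual ratio is 4.0 and the whole-rate RRs are 1.17, 1.32 and 1.46.

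If the qualifier covers the named events too, they are filtered as well. At p = 20% and 0.8 v 0.4, this gives 1 − (1 − 0.25 × 0.8)(1 − 0.20 × 0.8) = 32.8% v 1 − (1 − 0.25 × 0.4)(1 − 0.20 × 0.4) = 17.2%, an RR of about 1.9.

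**The case against.** The strongest reply is that little is lost. Death and other serious events are captured whatever their cause. Severe complications overlap heavily with the seriousness criteria of section 14.2, so the events at risk are a narrow set: residual, severe, and not serious. Hematoma expansion would be read on CT, and imaging is assessed blind. Both arms are described under interventions in section 9, so an event in a control patient can also be attributed. This stands, and it limits the size of the problem. It does not remove the conflict between section 14.1 and the sections that follow it.

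A reader might go further than the documents allow in four ways.

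- *That the complication rate depends on attribution.* Section 11.2 carries no relatedness condition, so the dependence arises only if its list is completed from section 14.1.
- *That attribution is unblinded.* Section 7.4 says that the staff giving oxygen are unblinded, not that they judge causality. Section 16 speaks of blinded assessors and blinded rechecking of data, without tying either to causality. The fair statement is that it is unspecified.
- *That the rule does filter differently by arm.* It can. No text shows that it did, and equal attribution would only under-count.
- *That the unrelated grades are empty, or that moderate events are lost through attribution.* The named events and SAEs can be graded unrelated, and moderate residual events are excluded by the severity word.

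**Conclusion.** The point holds as a defect of definition. Section 14.1 makes judged association a condition for residual complications to count as AEs. That contradicts the all-cause SAE definition and the causality grading that is meant to follow. Because the trial is open label and the causality judgement is neither assigned nor stated to be blinded, residual events short of SAE criteria can be under-counted or counted differently by arm. The effect on the complication rate is conditional on how the list in section 11.2 was completed.

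Confidence is high on the inconsistency and moderate on any effect on the reported rate. The size cannot be derived from the documents. Every ratio above follows from assumed event rates and attribution probabilities; the ratio of 2.0 belongs to the residual group, and the effect on the whole rate is smaller. The primary outcome is not touched. The correction is worth making because it replaces a rule that can distort a safety comparison with a standard definition.

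**What to change.** - In section 14.1, define an AE as any untoward medical occurrence from randomization onward, regardless of relatedness. Drop the restriction to severe events, since section 14.4.1 already grades severity.
- Keep pulmonary infection, acid-base imbalance and hematoma expansion as events of special interest.
- Record relatedness only as a separate attribute under section 14.4.2. State who judges it and whether that person is blinded to arm.
- In section 11.2, list the components of the complication rate. Tabulate the all-cause in-hospital rate by arm, with related events as a secondary table.

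The cost is a longer AE listing and higher reported event rates in both arms. Section 15.1 says that enrolment ended at 96 participants, so new wording alone cannot recover events that were never recorded; that would take a review of records. The report should give all-cause events where records allow. Otherwise it should state that the association filter was applied.

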14.2 Serious adverse events (SAEs)

SAEs are any untoward medical occurrence (whether related to interventions or not) meeting any of the following criteria: (1) fatal (AEs causes death); (2) life-threatening; (3) causing or prolonging hospitalization; (4) disability or organ function impairment.

14.3 Safety assessment

For AEs and SAEs occurring in this study, the following factors will be evaluated for safety: (1) severity criteria for AEs; (2) causal relationship between the event and intervention; (3) anticipation of events.

14.4 Severity categorization and relationship definitions of AEs

14.4.1 Severity categorization

(1) Grade I, mild

A transient symptoms or the event that requires only minimal therapeutic interventions. The event does not affect usual activities of daily living.

(2) Grade II, moderate

A significant symptoms or the event that requires additional specific therapeutic interventions. The event affect usual activities of daily living, causing discomfort or disability but with no profound or permanent risk of harm to the participant.

(3) Grade III, severe

A profoundly severe symptoms or the event that requires intensive therapeutic interventions. The event profoundly affects or interrupts usual activities of daily living, causing disability and even posing permanent risk of harm to the participant.

(4) Grade IV, life-threatening

The event leads to death at any time.

(5) Grade V, death

Death.

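### The Grade IV (life-threatening) definition in section 14.4.1 requires death, so it overlaps Grade V and gives a survived life-threatening event no grade of its own.

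*Combined protocol and SAP*

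**What the plan says.** Section 14.4.1 sets out a five-level severity scale. The fourth level is headed "4) Grade IV, life-threatening", and the only text under it is "The event leads to death at any time". The fifth is headed "5) Grade V, death", and its definition is that one word again. The level below, Grade III, covers severe events that need intensive treatment, "causing disability and even posing permanent risk of harm to the participant". It does not mention risk to life.

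Section 14.2 defines a serious adverse event by a list that begins "1) fatal (AEs causes death); (2) life-threatening; (3) causing or prolonging hospitalization". Fatal and life-threatening are separate items there. Section 14.3 makes "severity criteria for AEs" one of three factors to be evaluated for AEs and SAEs, alongside causality and anticipation. The scale is therefore meant to be applied. No other section gives a different definition of Grade IV.

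**The concern.** A severity scale has to put each event in one category, and two graders working from the text should choose the same one. Here the label and the definition of Grade IV point in different directions, and the protocol does not say which governs. A grader who follows the label puts a survived life-threatening event in Grade IV. A grader who follows the definition finds that it does not qualify and falls back on Grade III, or leaves it ungraded. For a fatal event, the definitions of both Grade IV and Grade V are met.

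Such events are foreseeable in this trial. Section 9 anticipates hematoma expansion with cerebral herniation, section 7.2.3 provides for acute respiratory disease and other severe complications during the intervention, and section 11.2 counts hematoma expansion and pulmonary infection as complications. What is at stake is whether the most severe non-fatal events are graded consistently in a trial that names safety among its objectives (section 6).

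**Working it through.** No arithmetic applies. The point depends on wording and on no rate, power or sample size, and the plan states no figure to reproduce. The check is to set the definitions side by side and run two kinds of event through them.

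| Source | Label or item | What the text requires |
|---|---|---|
| 14.4.1, Grade III | severe | intensive treatment, disability, permanent risk of harm; nothing on risk to life |
| 14.4.1, Grade IV | life-threatening | that the event leads to death; no word such as may, could or risk |
| 14.4.1, Grade V | death | death |
| 14.2, SAE item 1 | fatal | the event causes death |
| 14.2, SAE item 2 | life-threatening | separate from item 1 |

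**Event A: life-threatening, and the patient survives.** Under section 14.2 it is serious by "2) life-threatening". Under section 14.4.1 it fails the Grade V definition because there is no death, and fails the Grade IV definition for the same reason. The nearest definition it can meet is Grade III, which does not describe a threat to life. By label alone it belongs in Grade IV. Definition and label give different answers.

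**Event B: fatal.** Under section 14.2 it is serious by item 1. Under section 14.4.1 it meets the Grade IV definition and the Grade V definition. By label it belongs in Grade V.

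The next question is where the grade is used. Section 14.3 requires severity to be evaluated. The safety outcomes in section 11.2 are 7-day blood gases and pH, the death rate and the complication rate, and none is defined by grade. Section 15.2 specifies no analysis that uses grade. Section 14.2 decides seriousness by its own criteria, so event A is an SAE whichever grade it receives.

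**The case against.** The strongest reply is that the intended meaning is plain. Grades IV and V carry different labels, so IV must be the non-fatal one. The closing phrase of the Grade IV sentence adds little if death has already occurred, so the sentence probably meant that the event could lead to death. The same section has other slips of English, and section 14.2 shows that the authors distinguish the two ideas. This is fair, and it stands to this extent: the label still directs a survived life-threatening event to Grade IV, so it would be too strong to say that the scale has no place for one. It does not remove the defect, because the definition contradicts the label and a probable intention is not a written rule.

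The second reply is that little depends on the grade. That stands in full for the outcomes and analyses traced above.

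A reader might go further and infer that every survived life-threatening event was in fact misgraded, or that a Grade IV rate is off by some number of percentage points. The documents do not support either. They report no adverse event counts and no grades, and nothing shows which reading the graders used. With 48 patients per arm (section 15.1), one reclassified event would move an arm's rate by 1/48, about 2.1 percentage points, but that is true of any single event in any arm of 48 and says nothing about this scale.

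A reader might also infer that the DSMB was shown a faulty severity table. Section 17 says that safety and efficacy were assessed at an interim time-point. It does not mention adverse event grades or any table by grade.

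**Conclusion.** The definition of Grade IV is wrong as written. It conflicts with its own label, overlaps Grade V, and is out of line with section 14.2. This is an inconsistency of wording in an operative rule; nothing suggests a deliberate design choice.

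The impact is limited to descriptive severity grading of adverse events under section 14.3. SAE classification, the death rate, the complication rate, the primary outcome and the other efficacy analyses are unaffected. The conclusion rests on reading the Grade IV sentence literally and on the absence of any other definition in the documents. How many events were affected, if any, cannot be determined from them.

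**What to change.** Reword Grade IV as an event that puts the participant at immediate risk of death when it occurs but is not fatal. Keep Grade V for events that result in death. The two grades then exclude each other and match the separate items in section 14.2.

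Section 15.1 reports that enrolment ended at 96, so the new wording cannot guide grading of events during enrolment. Recheck events recorded as Grade III, IV or V against the corrected definition, and document each change with its reason. The recheck should be done by assessors blinded to allocation. The trial is open label, section 7.4 spells out blinded assessment for neurological scores and imaging only, and section 16, which says that assessors were blinded, does not mention event grading. Unblinded regrading after the fact could introduce bias.

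The cost is one sentence and a short retrospective check of a limited set of events. No outcome or efficacy analysis has to be rerun.

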14.4.2 Causal relationship between the event and the intervention

(1) Definitely related

AEs occur during the intervention and/or the AEs disappear when the intervention discontinues. The

occurrence of AEs cannot be explained by factors other than the intervention. Similar AEs re-occur when re-use of the intervention.

(2) Probably related

AEs occur during the intervention and/or the AEs relieve or not when the intervention discontinues. The occurrence of AEs can or cannot be explained by factors other than the intervention. It is not sure similar AEs re-occur when re-use of the intervention.

(3) Probably unrelated

AEs do not occur during the intervention and/or the AEs do not relieve when the intervention discontinues. The occurrence of AEs can or cannot be explained by factors other than the intervention. It is not sure similar AEs re-occur when re-use of the intervention.

(4) Definitely unrelated

AEs do not occur during the intervention and/or the AEs do not relieve when the intervention discontinues. The occurrence of AEs can be explained by factors other than the intervention. Similar AEs do not re-occur when re-use of the intervention.

(5) Unjudged

The judgment cannot be made due to incomplete information.

15. Statistics

